### *Analysis of Primary Endpoint (Change From Baseline in HBsAg Levels at Week 24)*

Within Part A and Part B, the magnitude of the effect of JNJ-56136379+NA as compared to placebo+NA will be evaluated using the posterior distribution of the treatment effect (difference between JNJ-56136379+NA and placebo+NA) obtained in a Bayesian analysis. This Bayesian analysis will incorporate historical data for the placebo+NA arm(s) in an informative MAP prior with robustness modifier. For the current sample size simulations, historical data comes from an ongoing systematic literature review on HBsAg declines during NA treatment, resulting in 20 studies including around 2,835 subjects. More details on the eventual historical data, including all references to all studies, will be provided in the Modeling and Simulation Report/SAP. For each study part and HBeAg status subgroup the appropriate historical prior will be used. Within Part A and Part B, JNJ-56136379+NA will also be compared with JNJ-56136379 as monotherapy but without including historical data as both arms include experimental treatments and appropriate historical data are consequently missing. In addition a similar analysis but without historical data in a frequentist approach will also be conducted as a sensitivity analysis.

The dose-response of JNJ-56136379 in an NA background regimen will be studied by a multiple contrast test (MCP) using 3 model-based contrasts covering the 3 possible shapes (linear, convex, and concave) with a control group (placebo+NA) and 2 doses. This analysis uses the data of these 3 treatment groups together to evaluate a dose-response signal, assuming a similar dose effect for each HBeAg subgroup and no difference in placebo+NA across Parts A and B. Sensitivity analyses will be done investigating differences across Parts A and B and differences between the two HBeAg subgroups.

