A Bayesian analysis will be conducted for Part A and Part B separately to compare the mean HBsAg change from baseline at Week 24 of JNJ-56136379 as monotherapy and in combination with NA versus placebo+NA by HBeAg subgroup. This Bayesian analysis will incorporate historical data for the placebo+NA arm(s) in an informative meta-analytic predictive (MAP) prior with robustness modifier. For the current sample size simulations, historical data comes from an ongoing systematic literature review on HBsAg declines during NA treatment, resulting in 20 studies including around 2,835 subjects. More details on the eventual historical data, including all references to all studies, will be provided in the Modeling and Simulation Report/SAP. The Bayesian equivalent of power, ie, the likelihood that the posterior probability that the mean change from baseline of HBsAg at Week 24 is larger in the JNJ-56136379+NA arm than in the placebo+NA arm is at least 90%, was determined. The results are summarized in [Table 7](#).

It is concluded that, under the assumptions made, the posterior distribution of the estimate of treatment difference between the placebo+NA and JNJ-56136379+NA arm will be precise enough to allow meaningful conclusions. The probability to detect a treatment effect with at least 90% confidence is 0.80 or higher for the HBeAg-negative subgroup in both subjects currently not being treated and virologically suppressed subjects. For the HBeAg-positive subgroup, power is substantially lower which increases the risk of inconclusive results. However, if the interim analysis at Week 12, Week 24 or Week 48 indicates no safety concerns and a potential benefit, a moderate sample size increase for HBeAg-positive subjects to a maximum of 6 subjects on placebo+NA and 18 subjects on JNJ-56136379 monotherapy and JNJ-56136379+NA per study part may be considered. This will increase the probability to detect a treatment effect in these subgroups from 64% or 57% to around 84%.

**Table 7: Bayesian Power Analysis for the Different Prior Treatment and HBeAg Status Subgroups: HBsAg Change From Baseline**

	HBeAg Status	HBsAg ( $\log_{10}$ IU/mL) Change From Baseline		Sample Size (Placebo+NA/JNJ-56136379+NA)	Power a
		Mean $\pm$ SD	Mean $\pm$ SD		
		Placebo+NA	JNJ-56136379+NA		
Currently not being treated	Positive	-0.35 $\pm$ 0.6	-1.35 $\pm$ 2.16	4/12 b	0.64
	Negative	-0.05 $\pm$ 0.4	-1.05 $\pm$ 2.16	6/18 b	0.84

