#### 11.3.1. Analysis of Primary Endpoint (Change From Baseline in HBsAg Levels at Week 24)

Within Part A and Part B, the magnitude of the effect of JNJ-56136379+NA as compared to placebo+NA will be evaluated using the posterior distribution of the treatment effect (difference between JNJ-56136379+NA and placebo+NA) obtained in a Bayesian analysis. This Bayesian analysis will incorporate historical data for the placebo+NA arm(s) in an informative MAP prior with robustness modifier. For the current sample size simulations, historical data comes from an ongoing systematic literature review on HBsAg declines during NA treatment, resulting in 20 studies including around 2,835 subjects. More details on the eventual historical data, including all references to all studies, will be provided in the Modeling and Simulation

Report/SAP. For each study part and HBeAg status subgroup the appropriate historical prior will be used. Within Part A and Part B, JNJ-56136379+NA will also be compared with JNJ-56136379 as monotherapy but without including historical data as both arms include experimental treatments and appropriate historical data are consequently missing. In addition a similar analysis but without historical data in a frequentist approach will also be conducted as a sensitivity analysis.

The dose-response of JNJ-56136379 in an NA background regimen will be studied by a multiple contrast test (MCP) using 3 model-based contrasts covering the 3 possible shapes (linear, convex, and concave) with a control group (placebo+NA) and 2 doses. This analysis uses the data of these 3 treatment groups together to evaluate a dose-response signal, assuming a similar dose effect for each HBeAg subgroup and no difference in placebo+NA across Parts A and B. Sensitivity analyses will be done investigating differences across Parts A and B and differences between the two HBeAg subgroups.

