### **5.2.1.2 Bayesian Efficacy Analysis**

For each of the comparisons listed above, a Bayesian approach will be employed. Non-informative priors will be used for the JNJ-56136379 arms. The prior for the mean of the placebo+NA treatment arms, on the other hand, will consist of a meta-analytic predictive (MAP) prior, derived from historical data. For the residual variance, a non-informative prior will be used for all treatments. To explore the robustness of the Bayesian analysis to a potential prior-data conflict, the analysis will be conducted with both full and no borrowing and the results compared.

A systematic review of published data on the HBsAg change from baseline at Week 24 in treatment of subject populations with NA (tenofovir, entecavir) has been carried out by Clinical Virology and Statistics & Decision Sciences. The respective MAP distributions for the different subject populations have been derived based on a pre-final version of this database. Since the MAP distributions are not of standard form, they are each approximated

---

as a mixture of normal distributions. The resulting normal mixtures, with corresponding component means and variances, are summarized in **Table 3**.

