**Table 3: Components of the normal mixtures (mean and variance) of the MAP by sub-population.**

Mixture Component	Currently Not Being Treated		Virologically Suppressed (applies to both HbeAg Negative /Positive)
	HBeAg Positive	HBeAg Negative	
1	0.7447 N(-0.3059, 0.01892)	0.0177 N(-0.01450, 0.1045)	0.3809 N(-0.06528, 0.01440)
2	0.2553 N(-0.3122, 0.05255)	0.5728 N(-0.00925, 0.005850)	0.6191 N(-0.05667, 0.004036)
3		0.4095 N(-0.01308, 0.01988)	

To facilitate description of the methodology, for the remainder of this section, the treatment arm containing JNJ-56136379 will be referred to as the experimental (E) arm, to be compared with the active comparator or standard of care (S) arm (i.e. placebo+NA arm).

The efficacy analysis of JNJ-56136379HPB2001 aims to demonstrate superiority of JNJ-56136379 in combination with NA therapy over NA therapy alone. Within a Bayesian framework, declaring superiority is based on the posterior probability

$$P(\theta_E^* - \theta_S^* < 0 | Y_E^*, Y_S^*, \mu_{E_{prior}}, \mu_{S_{prior}}, \tau_{E_{prior}}^2, \tau_{S_{prior}}^2), \quad (1)$$

where:

$Y_E^*$  and  $\theta_E^*$  respectively denote the observed and true mean change in serum HBsAg levels for the experimental arm in the current trial, JNJ-56136379HPB2001,

$Y_S^*$  and  $\theta_S^*$  respectively denote the observed and true mean change in serum HBsAg levels for the Control arm in the current trial, JNJ-56136379HPB2001,

$(\theta_E^* - \theta_S^*) \equiv \Delta$  denotes the treatment effect of JNJ-56136379 in combination with NA therapy over NA therapy alone for the current trial, JNJ-56136379HPB2001,

---

$\mu_{E_{prior}}$  and  $\tau_{E_{prior}}^2$  respectively denote the prior mean and prior variance for  $\theta_E^*$ , and

$\mu_{S_{prior_i}}$  and  $\tau_{S_{prior_i}}^2$  respectively denote the mean and variance of the  $i^{\text{th}}$  component of the mixture prior for  $\theta_S^*$ .

Since no historical efficacy data is available for the experimental arm, a non-informative normal prior distribution will be specified for  $\theta_E^*$ , that is  $\mu_{E_{prior}} = 0$  and  $\tau_{E_{prior}}^2 = 100$ . For the Control arm,  $\mu_{S_{prior_i}}$  and  $\tau_{S_{prior_i}}^2$  are the means and variances enumerated in **Table 3** for the corresponding subject population.

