Using Markov chain Monte Carlo (MCMC) methods, the posterior distribution for the treatment effect,  $(\theta_E^* - \theta_S^*) \equiv \Delta$ , of JNJ-56136379 in combination with NA therapy over NA therapy alone, will be derived using the MCMC procedure in SAS® (see Appendix for sample implementation). The posterior probability in (1) will be obtained from this posterior distribution of  $(\theta_E^* - \theta_S^*) \equiv \Delta$ .

The MCMC sampling will be initially run with 10,000,000 iterations (excluding 100,000 burn-in iterations) and thinning parameter of 100, specifying the seed as 123. Assessment of the convergence of the chain will be done using the built-in diagnostic tools of the MCMC procedure in SAS® (**See APPENDIX 1 for the SAS code**) Depending on the results of the diagnostic approaches, some of the MCMC settings may be modified to improve convergence.

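### The SAP takes its Bayesian superiority probability from the historical MAP prior without the robustness modifier that the protocol specifies, and records no change

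*SAP*

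**What the plan says.** The protocol synopsis states: "This Bayesian analysis will incorporate historical data for the placebo+NA arm(s) in an informative MAP prior with robustness modifier". Protocol 11.2 and 11.3.1 repeat this, and 11.3.1 adds: "For each study part and HBeAg status subgroup the appropriate historical prior will be used".

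SAP 5.2.1.2 says that the prior for the placebo+NA mean "will consist of a meta-analytic predictive (MAP) prior, derived from historical data". The MAP distributions "have been derived based on a pre-final version of this database" and are approximated by the normal mixtures in Table 3, whose caption describes them as the components of the MAP. Below the table the SAP says: "Within a Bayesian framework, declaring superiority is based on the posterior probability", numbered (1), with the Table 3 means and variances as the control prior. It continues: "The posterior probability in (1) will be obtained from this posterior distribution of" the treatment effect. To examine prior-data conflict, "the analysis will be conducted with both full and no borrowing and the results compared".

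The SAP reference list contains the robust-MAP paper, but no section defines a vague component, a weight or a variance for one. The SAP amendment history mentions no change to the prior.

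The Appendix 1 header names currently untreated HBeAg-positive subjects and gives their Table 3 mixture. The PROC MCMC statement below it loads the virologically suppressed mixture.

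**The concern.** A robustness modifier lets the analysis give less weight to the historical data when the trial's own controls disagree with them. Without it, borrowing continues at nearly the same strength however large the disagreement. Two features make this relevant here: each subgroup cell has only a handful of concurrent controls, and the prior was built before the historical database was final.

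If trial controls decline more than the published cohorts, the borrowed control mean is pulled upward and JNJ-56136379 looks better than it is. If they decline less, a real benefit is understated. The two documents therefore describe different priors for the primary endpoint, and the SAP's version gives less protection against drift.

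**Working it through.** **1. The plan's own power figures.** Protocol Table 7 gives Bayesian power of 0.64, 0.84, 0.57 and 0.89 for cells of 4/12, 6/18, 3/9 and 7/21 (control/active). With the Table 3 priors, normal data and the 90% criterion from protocol 11.2, simulation gives 0.59, 0.74, 0.51 and 0.77. With assumed skewed mixtures (20–30% responders) it gives 0.63–0.64, 0.81–0.86, 0.43–0.50 and 0.87–0.88. The protocol does not publish its simulation mixture or a robust weight, so Table 7 can be neither confirmed nor faulted.

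**2. Weight of the prior.** Inputs are the Table 3 mixtures and the Table 7 placebo SDs. Mixture mean = Σwμ. Variance = Σw(variance + μ²) − mean². Effective sample size (ESS) = placebo SD² / prior variance. Share of control information = ESS / (ESS + n).

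| Cell | Prior mean | Prior SD | ESS | Concurrent n | Share |
|---|---|---|---|---|---|
| Untreated HBeAg+ | −0.3075 | 0.166 | 0.36/0.0275 ≈ 13 | 4 | 13/17 = 76% |
| Untreated HBeAg− | −0.0109 | 0.116 | 0.16/0.0133 ≈ 12 | 6 | 12/18 = 67% |
| Suppressed HBeAg+ | −0.0599 | 0.089 | 0.16/0.0080 ≈ 20 | 3 | 20/23 = 87% |
| Suppressed HBeAg− | −0.0599 | 0.089 | ≈ 20 | 7 | 20/27 = 74% |

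**3. How much of a gap reaches the estimate.** Drift is the trial control mean minus the prior mean. The simulations use 4,000 replicates per cell, normal data and an inverse-gamma(0.01, 0.01) prior on the variance. The example robust prior is 0.8 × MAP + 0.2 × a normal with one-observation variance. The 20% weight, that variance and all drift sizes are assumptions. At drift −0.2 the mean bias in the effect is:
- MAP: −0.14 to −0.18, that is 0.14/0.2 = 70% to 0.18/0.2 = 90% of the gap.
- Example robust prior: −0.11 to −0.14, that is 55% to 70%.
- No borrowing: about 0.

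**4. Chance of a posterior probability of at least 90% with no true effect.** The range is over the four cells. The 90% line is the protocol's sample-size criterion, not an SAP rule.

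| Scenario | MAP | Example robust | No borrowing |
|---|---|---|---|
| No drift, active SD 2.16 | 0.09–0.11 | 0.09–0.10 | 0.08–0.10 |
| Drift −0.2, active SD 2.16 | 0.13–0.17 | 0.12–0.15 | 0.08–0.10 |
| Drift −0.4, active SD 2.16 | 0.20–0.26 | 0.16–0.18 | 0.07–0.09 |
| Drift −0.2, active SD = control SD | 0.23–0.49 | 0.18–0.33 | 0.07–0.09 |

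The documents' own gaps (Table 7 control mean minus Table 3 prior mean) are −0.35 + 0.3075 = −0.04, −0.05 + 0.0109 = −0.04 and −0.05 + 0.0599 = +0.01. At these gaps the MAP gives 0.09–0.11, so there is no material inflation if the planning means hold.

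**5. Appendix 1.** On the sample data labelled as a small difference (12 active, 4 control), the probability that the effect is below 0 is:

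| Control prior | Probability |
|---|---|
| Header prior (untreated HBeAg+) | 0.913 |
| Header prior with the 20% robust component | 0.908 |
| No borrowing | 0.844 |
| Coded prior (virologically suppressed) | 0.986 |

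The printed code refers to variables that are absent from the sample dataset, so the last figure is the coded prior applied to those data, not output from the code as printed.

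**The case against.** The strongest reply is that a conflict would not stay hidden. The SAP prespecifies a no-borrowing run (5.2.1.2), an MMRM against the concurrent control (5.2.1 and 5.2.1.1) and a frequentist sensitivity analysis without historical data (5.2.1.3). That stands as to detection. None of the three alters probability (1), which still comes from the full MAP prior.

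A MAP prior is also already discounted for differences between studies. The protocol's sample-size review covered about 2,835 historical subjects, yet the Table 3 priors are worth only 12 to 20. Under those priors, a control mean at least 0.2 below the prior mean has probability 10%, 4% and 2% (untreated HBeAg+, untreated HBeAg−, suppressed). For 0.4 it is 1.2%, 0.3% and 0.02%. The larger drift scenarios are therefore remote if the prior is right, and the documents give no evidence that it is wrong.

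The protocol sends details of the historical data to a modeling and simulation report or the SAP. That report is not available, and it may discuss the modifier. The SAP nevertheless defines the control prior in (1) as the Table 3 components.

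A reader might infer more than the documents support:
- That weights summing to 1 in Table 3 prove the robust component is absent. They do not, because a robust mixture also sums to 1. The evidence is the SAP's description of the mixtures as approximations of the MAP.
- That 0.913 against 0.844 shows the missing modifier matters. That contrast is borrowing against no borrowing; the robust prior gives 0.908, on the same side of 90% as the MAP.
- That the lack of a posterior cut-off, or of a rule for runs that disagree, is itself a defect. SAP 1.4 says there is no formal hypothesis testing, and the SAP reports posterior percentiles and three probabilities. This is missing detail, not a ground for this point.

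**Conclusion.** The discrepancy is real: the protocol names a robustness modifier for the primary-endpoint prior, while the SAP defines none and records no change. Whether the omission was intended cannot be told from the documents.

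Its practical size is modest. The prior supplies 67–87% of the control information, so most of any drift reaches the estimated effect. The example robust prior reduces that share from about 70–90% to about 55–70%; it does not remove it. A reader might infer a serious false-positive problem, but the figures do not support that at planning values. Without drift, restoring the modifier makes a negligible difference, and at −0.2 drift with active SD 2.16 it gains 1–2 points. Larger gains need an assumed bigger drift or an active SD well below the planned 2.16.

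The Appendix 1 mismatch is a separate template error. The appendix is labelled a sample, but if the code were reused unchanged it would apply the wrong population's prior, giving 0.99 instead of 0.91 on the sample data.

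**What to change.** - Add the protocol's robust component to each Table 3 prior, with a prespecified weight and variance. Base probability (1) on it, and keep full and no borrowing as sensitivity analyses.
- If the omission was intended, record it in the SAP as a change from the protocol, with the reason.
- In Appendix 1, load the Table 3 mixture for the population being analysed, and correct the comment lines that pair the suppressed weights with the untreated HBeAg+ means and SDs.
- Optionally, reconcile the superiority wording in 5.2.1.2 with the statement in SAP 1.4 that there is no formal hypothesis testing.

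These are edits to SAP text, one table and code; trial conduct is unaffected. At planning values (effect −1, active SD 2.16) simulated power moves from 0.59, 0.74, 0.51 and 0.77 with the MAP to 0.58, 0.74, 0.50 and 0.76 with the example robust prior, a loss of 0.01 or less. With an effect of −0.5 and equal SDs the loss reaches about 0.06. The 20% weight and one-observation variance are an illustration; the sponsor should choose and justify its own.

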**Table 3: Components of the normal mixtures (mean and variance) of the MAP by sub-population.**

Mixture Component	Currently Not Being Treated		Virologically Suppressed (applies to both HbeAg Negative /Positive)
	HBeAg Positive	HBeAg Negative	
1	0.7447 N(-0.3059, 0.01892)	0.0177 N(-0.01450, 0.1045)	0.3809 N(-0.06528, 0.01440)
2	0.2553 N(-0.3122, 0.05255)	0.5728 N(-0.00925, 0.005850)	0.6191 N(-0.05667, 0.004036)
3		0.4095 N(-0.01308, 0.01988)	

To facilitate description of the methodology, for the remainder of this section, the treatment arm containing JNJ-56136379 will be referred to as the experimental (E) arm, to be compared with the active comparator or standard of care (S) arm (i.e. placebo+NA arm).

The efficacy analysis of JNJ-56136379HPB2001 aims to demonstrate superiority of JNJ-56136379 in combination with NA therapy over NA therapy alone. Within a Bayesian framework, declaring superiority is based on the posterior probability

$$P(\theta_E^* - \theta_S^* < 0 | Y_E^*, Y_S^*, \mu_{E_{prior}}, \mu_{S_{prior}}, \tau_{E_{prior}}^2, \tau_{S_{prior}}^2), \quad (1)$$

where:

$Y_E^*$  and  $\theta_E^*$  respectively denote the observed and true mean change in serum HBsAg levels for the experimental arm in the current trial, JNJ-56136379HPB2001,

$Y_S^*$  and  $\theta_S^*$  respectively denote the observed and true mean change in serum HBsAg levels for the Control arm in the current trial, JNJ-56136379HPB2001,

$(\theta_E^* - \theta_S^*) \equiv \Delta$  denotes the treatment effect of JNJ-56136379 in combination with NA therapy over NA therapy alone for the current trial, JNJ-56136379HPB2001,

---

$\mu_{E_{prior}}$  and  $\tau_{E_{prior}}^2$  respectively denote the prior mean and prior variance for  $\theta_E^*$ , and

$\mu_{S_{prior_i}}$  and  $\tau_{S_{prior_i}}^2$  respectively denote the mean and variance of the  $i^{\text{th}}$  component of the mixture prior for  $\theta_S^*$ .

Since no historical efficacy data is available for the experimental arm, a non-informative normal prior distribution will be specified for  $\theta_E^*$ , that is  $\mu_{E_{prior}} = 0$  and  $\tau_{E_{prior}}^2 = 100$ . For the Control arm,  $\mu_{S_{prior_i}}$  and  $\tau_{S_{prior_i}}^2$  are the means and variances enumerated in **Table 3** for the corresponding subject population.

Using Markov chain Monte Carlo (MCMC) methods, the posterior distribution for the treatment effect,  $(\theta_E^* - \theta_S^*) \equiv \Delta$ , of JNJ-56136379 in combination with NA therapy over NA therapy alone, will be derived using the MCMC procedure in SAS® (see Appendix for sample implementation). The posterior probability in (1) will be obtained from this posterior distribution of  $(\theta_E^* - \theta_S^*) \equiv \Delta$ .

The MCMC sampling will be initially run with 10,000,000 iterations (excluding 100,000 burn-in iterations) and thinning parameter of 100, specifying the seed as 123. Assessment of the convergence of the chain will be done using the built-in diagnostic tools of the MCMC procedure in SAS® (**See APPENDIX 1 for the SAS code**) Depending on the results of the diagnostic approaches, some of the MCMC settings may be modified to improve convergence.

#### ➤ Summary of the posterior distribution

The posterior distribution of  $(\theta_E^* - \theta_S^*) \equiv \Delta$  will be summarized using: mean, median, standard deviation, 5th, 10th, 20th, 50th, 80th, 90th, 95th percentiles, posterior probability that the Week 24 change is smaller than 0, smaller than -0.5 and smaller than -1.

A density function of the posterior distribution will also be plotted.

---

### 5.2.1.3 Sensitivity Analysis

In addition, a similar analysis but without historical data in a frequentist approach will also be conducted as a sensitivity analysis for both part A and B using all population in ITT population at week 24 and will be conducted to compare:

- The mean of HBsAg change from baseline in log 10 transformed at week 24 of JNJ-56136379 monotherapy (open label) versus placebo+NA
- The mean of HBsAg change from baseline in log 10 transformed at week 24 of JNJ-56136379+NA versus placebo+NA
- The mean of HBsAg change from baseline in log 10 transformed at week 24 of JNJ-56136379 as monotherapy (open label) versus JNJ-56136379+NA

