**Part A:**

Approximately 70 subjects who are currently not being treated for their CHB infection will be randomized in a 3:1:3 ratio to receive one of the following treatments:

- Treatment Arm 1: JNJ-56136379 (N=30) (open-label)

After full recruitment, this treatment arm was discontinued early per Protocol Amendment 4. All subjects were to stop further dosing with JNJ-56136379 75 mg, start treatment with NA, and enter the post-treatment follow-up phase (Schedule 1).

- Treatment Arm 2: Placebo + NA (ETV or TDF) (N=10)
- Treatment Arm 3: JNJ-56136379 + NA (ETV or TDF) (N=30)

At the same time, approximately 40 subjects who are virologically suppressed by current NA treatment will be randomized in a 1:3 ratio to receive one of the following treatments:

- Treatment Arm 4: Placebo + NA (ETV or TDF) (N=10)
- Treatment Arm 5: JNJ-56136379 + NA (ETV or TDF) (N=30)

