## **2.6. Presentation of results**

Continuous parameters will be summarized using the following statistics: number of observations, mean, 95% confidence interval (CI) for mean, standard deviation (SD), standard error (SE), minimum, median and maximum, unless specified otherwise. The minimum and maximum will be presented to the same number of decimal places as the original data. The mean and median should be expressed with 1 decimal place more than the original values. The standard deviation, standard error and 95% confidence limits will be shown with 2 decimal place more than the original values.

Frequencies and percentages will be used for summarizing categorical (discrete) data. If a count is 0, the 0 count will be displayed, but the corresponding percentage should be omitted. If the corresponding denominator for the count is also 0, a hyphen (-) should be displayed rather than a 0 count or NAP [not applicable], and the corresponding percentage should be omitted.

---

All tables and graphs will be evaluated by subject population (i.e., subjects currently not being treated, virologically suppressed by current NA treatment or all population), by hepatitis B e antigen (HBeAg) status and overall, by treatment group (i.e., JNJ-56136379 [at two dose levels] and NA [entecavir {ETV} or tenofovir disoproxil fumarate {TDF}]) as monotherapy or coadministered), unless otherwise specified. Data will be presented in listings by subject population, HBeAg status, treatment group and subject number.

The main layout for the tables, unless specified otherwise, will be as followed:

Layout 1	Pooled Placebo + NA	JNJ6379 75 mg	JNJ6379 75 mg + NA	All JNJ6379 75mg	JNJ6379 250 mg	JNJ6379 250 mg + NA	All JNJ6379 250 mg	All JNJ6379 Doses

Layout 2	Pooled Placebo + NA	Placebo + NA Part A	Placebo + NA Part B

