## **5.2. Primary efficacy analysis**

The primary efficacy endpoint is the qualitative measurement of the viral activity parameter hepatitis B surface antigen (HBsAg) determined using standard serologic assays in a central laboratory.

Descriptive statistics (specified in section 2.6) and the comparison of the efficacy of 24 weeks treatment (i.e. combinations of JNJ-56136379 monotherapy, JNJ-56136379+NA and placebo+NA) is mainly of interest. These comparisons will be done overall, by subject population (i.e., subjects currently not being treated or virologically suppressed by current NA treatment), and by HBeAg status (Positive or Negative).

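### Monotherapy, given only to currently untreated subjects, is compared in the all-population analyses with arms that are half virologically suppressed, so those two contrasts are confounded with population

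*SAP*

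**What the plan says.** Protocol 3.1 sets up two separate randomisations in Part A. In the first, "Approximately 70 subjects who are currently not being treated for their CHB infection will be randomized in a 3:1:3 ratio", which gives 30 on monotherapy (Arm 1), 10 on placebo+NA (Arm 2) and 30 on JNJ-56136379+NA (Arm 3). In the second, "approximately 40 subjects who are virologically suppressed by current NA treatment will be randomized in a 1:3 ratio", which gives 10 on placebo+NA (Arm 4) and 30 on JNJ-56136379+NA (Arm 5). Part B repeats this format as Arms 6 to 10. Inclusion criteria 4 and 5 tie Arms 1-3 and 6-8 to untreated subjects, and Arms 4-5 and 9-10 to suppressed subjects.

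SAP 5.2.1.3 describes a frequentist analysis without historical data, "using all population in ITT population at week 24", for both parts. Its list includes "monotherapy (open label) versus placebo+NA" and "as monotherapy (open label) versus JNJ-56136379+NA". It names no model, no restriction by subject population and no adjustment for it.

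SAP 2.6 shows what the population term means. In listing the levels of subject population it ends with "virologically suppressed by current NA treatment or all population", a third level that combines the other two. SAP 5.2 adds "These comparisons will be done overall, by subject population", and protocol 11.3 says the same of the three main comparisons.

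The main analyses are set out differently. SAP 5.2.1.1 makes its comparisons within categories of subject population and HBeAg status and runs the MMRM by subject population. SAP 5.2.1.2 applies the Bayesian analysis to those same comparisons.

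**The concern.** No suppressed subject could be assigned to monotherapy. Once the populations are combined, the monotherapy group is entirely untreated while each comparator is half suppressed. That half was not randomised against monotherapy, and it differs by design in treatment history and viral load. Any difference between the populations in HBsAg change is then carried into the estimated treatment contrast.

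The check also loses part of its purpose. Protocol 11.3.1 presents it as an analysis similar to the Bayesian one but without historical data. For monotherapy versus placebo+NA, the SAP version removes the prior and changes the population at the same time. If the two results disagreed, the disagreement could not be put down to the prior.

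**Working it through.** **Planned sizes reproduced.** 70 × 3/7, 1/7, 3/7 = 30/10/30, and 40 × 1/4, 3/4 = 10/30, for a total of 110 per part as stated. With 40% HBeAg-positive in untreated and 30% in suppressed subjects, the placebo+NA/JNJ-56136379+NA cells are 4/12, 6/18, 3/9 and 7/21, as in protocol Table 7.

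**Composition per part, all subjects combined**

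| Arm | Untreated | Suppressed | Share suppressed |
|---|---|---|---|
| Monotherapy | 30 | 0 | 0 |
| Placebo+NA | 10 | 10 | 1/2 |
| JNJ-56136379+NA | 30 | 30 | 1/2 |

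**Formula.** Suppose monotherapy does exactly as well as the comparator in the same kind of patient. The combined contrast then still shows: share suppressed × (untreated mean − suppressed mean). With a share of 1/2 this is half the difference between the populations. A negative value favours monotherapy.

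**Protocol Table 7 means (log10 IU/mL)**
- Placebo+NA, untreated: 0.4 × (−0.35) + 0.6 × (−0.05) = −0.17. Suppressed: −0.05. Pooled 1:1: −0.11. Shift: −0.17 − (−0.11) = −0.06.
- JNJ-56136379+NA, untreated: 0.4 × (−1.35) + 0.6 × (−1.05) = −1.17. Suppressed: −1.05. Pooled: −1.11. Shift: −0.06.

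**SAP Table 3 prior (MAP) means, placebo+NA**
- Untreated HBeAg-positive: 0.7447 × (−0.3059) + 0.2553 × (−0.3122) = −0.308.
- Untreated HBeAg-negative: 0.0177 × (−0.01450) + 0.5728 × (−0.00925) + 0.4095 × (−0.01308) = −0.011.
- Suppressed: 0.3809 × (−0.06528) + 0.6191 × (−0.05667) = −0.060.
- Untreated overall: 0.4 × (−0.308) + 0.6 × (−0.011) = −0.130. Pooled with suppressed: −0.095. Shift: about −0.035.

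**HBeAg-negative subjects only.** The comparator has 6 untreated and 7 suppressed subjects. At the prior means its pooled value is (6 × (−0.011) + 7 × (−0.060))/13 = −0.037. The shift is −0.011 + 0.037 = +0.026, against monotherapy. At Table 7 values both groups have −0.05 and the shift is zero. The averaged shift in favour of monotherapy therefore comes from the HBeAg-positive assumption.

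**Effect on a nominal test.** Assume monotherapy behaves exactly like placebo+NA, with the Table 7 control SDs. The mixture SDs are:
- untreated: √(0.4 × 0.36 + 0.6 × 0.16 + 0.4 × 0.6 × 0.30²) = 0.511;
- pooled comparator: √(0.2 × 0.36 + 0.8 × 0.16 + 0.2 × 0.8 × 0.30²) = 0.463.

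The SE for 30 versus 20 is √(0.511²/30 + 0.463²/20) = 0.139. A shift of 0.06 is 0.43 SE, which takes a two-sided 5% error rate to about 7% per part. With both parts pooled (60 versus 40) it is about 9%.

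**Precision after restriction**, assuming monotherapy has the Table 7 JNJ-56136379+NA SD of 2.16:
- Versus placebo+NA: √(2.16²/30 + 0.463²/20) = 0.41 becomes √(2.16²/30 + 0.511²/10) = 0.43.
- Versus JNJ-56136379+NA: √(2.16²/30 + 2.16²/60) = 0.48 becomes √(2 × 2.16²/30) = 0.56.

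**The case against.** The strongest reply is that the right contrasts are already planned. The MMRM and Bayesian analyses work within subject population and include monotherapy, the study is exploratory with no formal hypothesis testing, and no decision rests on this sensitivity analysis. SAP 5.2.1.2 also runs the Bayesian analysis with and without borrowing, so the influence of the prior can be seen there. All of this stands, and it limits the point to one sensitivity analysis and the overall comparisons.

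A second reply is that the wording is ambiguous. The analysis is called similar to the by-population one, SAP 5.3 uses overall to mean pooled over HBeAg status, and SAP 2.5 gives an all-subjects level only for HBeAg. Each population in turn may have been meant. However, SAP 2.6 lists the combined level beside the two populations, and SAP 5.2 sets overall beside by-population comparisons. The text as written supports the combined reading, and if another was meant the SAP should say so.

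Three stronger readings might be inferred, and the documents do not support them.
- **Nothing in the combined analysis is randomised.** Half of each comparator was concurrently randomised against monotherapy. JNJ-56136379+NA versus placebo+NA has the same 1:3 allocation in both populations, so the mix does not bias it.
- **The bias always flatters monotherapy.** The HBeAg-negative calculation shows that it can reverse.
- **A very large bias in HBV DNA follows, because suppressed subjects have little left to lose.** SAP 5.2.1.3 covers HBsAg only, and the secondary MMRM is by subject population and part. The decline the protocol quotes is a four-week result for JNJ-56136379 itself, which cannot be carried over to a Week 24 NA comparison.

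**Conclusion.** The point holds for the two monotherapy contrasts in the combined population: monotherapy versus placebo+NA and monotherapy versus JNJ-56136379+NA. As written, both are confounded with subject population.

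At the documents' own planning values the bias averaged over HBeAg status is 0.035 to 0.06 log10. That is at most 6% of the planned 1.0 log10 effect and about 0.15 of an SE of 0.41. These figures assume the planned arm sizes and HBeAg mix, and the Table 7 or prior means. The size scales with the real difference between populations: a difference of 0.3 log10 would give 0.15. The by-population MMRM and Bayesian results need no change. This is a correction worth making to a secondary analysis and does not threaten the main conclusions.

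**What to change.** In SAP 5.2.1.3, and for the overall comparisons in SAP 5.2 and protocol 11.3, state that every comparison involving monotherapy is restricted to subjects not currently being treated, within part: Arm 1 versus Arms 2 and 3, and Arm 6 versus Arms 7 and 8. State also that only JNJ-56136379+NA versus placebo+NA is estimated in all subjects as well, stratified by subject population.

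Adding subject population as a covariate is not an adequate substitute. With no suppressed subjects on monotherapy, the adjusted contrast would rest on assuming no treatment-by-population interaction.

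The change is to wording, in the SAP and in one section of the protocol. The statistical cost is smaller comparators (10 instead of 20, and 30 instead of 60, per part) and the modest loss of precision shown above. In return, both contrasts are randomised ones and the sensitivity analysis uses the same population as the Bayesian analysis it is meant to check.
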